5 OBJECTIVES AND ENDPOINTS

All endpoints will be evaluated at the time points specified in the Schedule of Events at the beginning of **Section 9**. See **Section 12** for Statistical Methods and Data Analysis. Key comparisons will be the change from Day 1 (week 1) to Day 113 (week 17), which corresponds to the end of the 16 week exercise training program for Arm B, and from Day 1 (week 1) to Day 252 (week 37), which corresponds to the end of the 32 weeks of treatment with enzalutamide and ADT for both Arms.

	Objective	Endpoint	Analysis
Primary	Compare cardiopulmonary function in usual care vs. exercise training arms	Change in $\text{VO}_{2\text{peak}}$ with usual care or exercise training at 16 weeks from baseline	See Section 12.1 to 12.4
Key Secondary	Compare the effects on physical functioning / functional capacity	Objective assessments (i.e., chair-stand test, timed up and go, 6 minute walk distance) of functional capacity	See Section 12.5
Other Secondary	Compare the effects on primary physiological determinants of $\text{VO}_{2\text{peak}}$	Upper and lower extremity maximal muscular strength (voluntary one-repetition maximum [1-RM]) and muscular endurance (repetitions to fatigue at 70% of 1-RM and muscle cross sectional area of the dominant thigh (3.0 T magnetic resonance imaging)	See Section 12.5
Other Secondary	Compare the effects on metabolic outcomes of interest	Metabolic control (fasting glucose, insulin, glycosylated hemoglobin, HOMA-IR) and body composition (lean and fat body mass)	See Section 12.5
Other Secondary	Compare the effects on patient reported outcomes (PROs) of interest	Quality of Life (FACT-P), Fatigue (FACIT-F), and Leisure Time Exercise Habits (Godin Leisure Time Exercise Questionnaire)	See Section 12.5
Other Secondary	Evaluate safety, feasibility, and acceptability of exercise training	Eligibility rate, acceptance rate, adherence rate, attrition rate, and adverse event rate (CTCAE v4.0) in each arm	See Section 12.5
Exploratory	Compare PSA response rates	Maximum decrease in PSA from baseline (waterfall plot)	See Section 12.5
Exploratory	Describe metabolomics changes	Targeted and untargeted metabolic profiling	See Section 12.5
Sensitivity	Assay the robustness of results observed in analyses based on the modified ITT population	Primary and Key secondary endpoints, using Last Observation Carried Forward methods	See Section 12.5

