9.6 Treatment Period 1: ENZ-ADT plus either Usual Care or Exercise Training

Arm A, ENZ – ADT plus Usual Care: Beginning on Day 29 (week 5), subjects will be treated with androgen deprivation therapy (ADT) per standard of care (orchiectomy, GnRH agonist, or GnRH antagonist to maintain total testosterone <50 ng/dl for the remaining 32 weeks of the study). In addition, subjects will take enzalutamide (ENZ) 160 mg by mouth daily for the remaining 32 weeks of the study. The dosing of both the GnRH agonist and enzalutamide (160 mg daily) is the standard-of-care dosing. The treatment duration of approximately 8 months was selected to achieve maximal efficacy while minimizing toxicity and is based on intermittent hormonal therapy regimens studied in Phase III clinical trials.^{22,23} Concomitant medication will be evaluated at every clinic visit during enzalutamide therapy. Concomitant medications include all vitamins, herbal remedies, over the counter, and prescription medications.

Arm B, ENZ – ADT plus Exercise Training: Beginning on Day 29 (week 5), Subjects randomly allocated to this group will receive the same ADT-ENZ regimen as described above. In addition, subjects will continue the defined exercise training initiated during the Lead-In Period for a total of 16 weeks (through Day 113, week 17).

The window is ± 7 days for this period, EXCEPT Day 29 (week 5) which has a window of ± 3 days. See **Schedule of Events**, above.

Subject data to be collected during Treatment Period 1 includes:

- Physical Exam
- Height, Weight, BMI
- Vital Signs
- Performance Status (ECOG)
- Concomitant Medications
- Adverse Events
- CBC with Platelets (hemoglobin, hematocrit, platelet count, white blood cell count, total [absolute] neutrophils)
- Serum Chemistry (sodium, potassium, chloride, total CO₂ [bicarbonate], calcium, BUN, creatinine, glucose, albumin, total bilirubin, total protein, alkaline phosphatase, AST, ALT)
- Testosterone (Day 57 and 113)
- PSA
- CPET (Day 29 and Day 113)
- Chair Stand (Day 113)
- Timed Up and Go (Day 113)
- 6 Minute Walk Distance (Day 113; **Duke patients only**)
- Muscular Strength (*at least 24 hours before or after CPET on Week 4, Week 10 (not in conjunction with CPET) and week 17 in treatment period 2*)
- Muscle CSA (MRI; Day 113; **protocol v1-v15 only**)
- Muscular Endurance (*must be at least 24 hours before or after CPET to allow for adequate recovery on week 4, week 10 (not in conjunction with CPET) and week 17 in treatment period 2*)

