9.12.3 Correlative Assessments

All Correlative Assessments will be performed at Day 1 and Day 113 (see Schedule of Events at the beginning of this Section for details). Patient reported outcomes will also be performed at Day 252. In addition, a CPET will be performed at Day 29 to assess VO₂peak changes during the Lead-In Period and Metabolomics samples will be drawn at Day 57 to assess for early changes that may predict later changes in metabolic parameters. All samples will be collected in the fasting, pre-exercise state unless otherwise noted below.

Cardiopulmonary Exercise Testing (CPET)

Exercise Capacity will be assessed using a symptom-limited CPET on a motorized treadmill with expired gas analysis to determine VO₂peak, according to guidelines for clinical populations.⁹⁰ All CPET data will be recorded as the highest 30s value elicited during the CPET. During exercise, heart rate and rhythm will be monitored continuously using a 12-lead ECG. Equipment with similar technical specifications will be used across the two study sites to ensure reasonably accurate and precise results.

Physical Functioning / Functional Capacity

Physical Functioning / Functional Capacity will be assessed using the following assessments: chair-stand test, timed up and go, and 6 min walk distance outcomes as described previously.^{91 57,92,93} These measures will complement the exercise capacity measure.

Chair-Stand Test: The 5-repetition chair-stand test measured the time taken to complete 5 repetitions of the sit-to-stand maneuver. All sit-to-stand maneuvers will be performed from a chair without an arm rest at 43cm in height and 47.5cm in depth. Standardized instructions will be provided as follows: "By the count of 3, please stand up and sit down as quickly as possible for

5 times. Place your hands on your lap and do not use them throughout the procedure. Lean your back against the chair's backrest at the end of every repetition." Timing will start when the subject's back left the backrest and will be stopped once the back touched the backrest.

Timed Get Up and Go: Subjects will be required to stand up from a chair with armrests, walk 3m, turn around, return to the chair, and sit down. The time taken to complete this task will be measured in seconds with a stopwatch.⁹³

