12.1 Analysis Sets

The intent-to-treat (ITT) population will consist of all randomized patients. The modified intent-to-treat (ITT) population will consist of all randomized patients who have both a baseline and week 17 evaluation. In the ITT analyses and the modified ITT analyses patients will be analyzed according to the study arm to which they were randomized. The modified ITT population will be the primary analysis population.

The per-protocol population will consist of all randomized patients with both baseline and week 17 measurements for the primary endpoint and prior to any analysis: have been deemed compliant and properly evaluated for efficacy per investigator, satisfied all inclusion and exclusion criteria, and correctly assigned treatment.

The safety population will be all patients with at least one safety evaluation.

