12.4.3 Handling of missing values, censoring, and discontinuations

The primary analysis from baseline to week 17 will include only complete cases.

Patients without VO_2peak measured at week 17 who have one or more measurements during the period from week 17 to the end of week 36 will have their week 17 measurement estimated by interpolation from the end of week 4 to the closest measurement following week 17. A sensitivity analysis will be done including these patients with complete cases.

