For analysis of metabolomics, PCA analysis will be used to reduce the large number of correlated factors into a smaller number of dimensions. Unless otherwise noted, all analyses will be done separately for the usual care and exercise groups. Of primary interest is the association of metabolomic biomarkers with changes in both VO₂peak and HOMA-IR. Changes in metabolite concentrations and VO₂peak or HOMA-IR will be compared between the usual care and exercise groups using ANOVA. Correlation analysis and linear regression will be used to describe the relationship between metabolomics biomarker changes and VO₂peak or and HOMA-IR. Nominal statistical significance will be defined as p<0.05.

In addition, the maximum PSA change from baseline in each patient will be described using waterfall plots. The PSA response rate, defined as the proportion of men with a ≥80% decline in PSA from baseline, will be reported for each arm. The median decrease in PSA will also be reported for each arm.

Sensitivity analyses will be performed repeating primary endpoint and key secondary endpoint analyses using Last Value Carried Forward (LOCF) methods. The intent of this sensitivity analysis is to assay the robustness of results observed in the modified ITT population.

Adjustment for multiple comparisons is not planned for secondary or exploratory measures.

Rates of adverse events, classified by CTCAE v4.0, will be displayed by body system and preferred term for each arm.

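### For men with no week-17 test, LOCF can only carry forward a value from before enzalutamide plus ADT, so agreement with the complete-case result does not show robustness; the bias can go either way

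*Combined protocol and SAP*

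**What the plan says.** The primary comparison of the change in VO2peak rests on men with both measurements. Section 12.1 defines the set: "The modified intent-to-treat (ITT) population will consist of all randomized patients who have both a baseline and week 17 evaluation". Section 12.4.3 adds: "The primary analysis from baseline to week 17 will include only complete cases".

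Section 12.5 then provides the check: "Sensitivity analyses will be performed repeating primary endpoint and key secondary endpoint analyses using Last Value Carried Forward (LOCF) methods". Its purpose is stated there ("The intent of this sensitivity analysis is to assay the robustness of results observed in the modified ITT population") and again in the Sensitivity row of the Section 5 table ("Assay the robustness of results observed in analyses based on the modified ITT population").

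The test dates settle what can be carried forward:

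- **VO2peak.** Baseline exercise testing (Section 9.3) includes a CPET. After that, Section 9.6 lists "CPET (Day 29 and Day 113"), and Section 9.12.3 explains that "a CPET will be performed at Day 29 to assess" changes over the lead-in. Enzalutamide plus ADT starts on Day 29 in both arms (Section 9.6). Section 12.4.2 itself reads the change to the end of week 4 as the effect of exercise or usual care alone.
- **Key secondary tests.** Section 9.6 lists "Chair Stand (Day 113"), and likewise timed up-and-go and 6-minute walk (Duke only) at Day 113. The only earlier measurement is baseline.
- **Early withdrawal and later visits.** The premature-withdrawal visit is the Safety Follow-Up visit (Section 9.11.2). Neither the Schedule of Events nor Section 9.7 lists a CPET or functional test there or at any visit after Day 113.

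**The concern.** Men who stop training but are still tested at Day 113 are already in the primary analysis. LOCF can change the result only by adding men with no week-17 test, so its value depends on what it assigns to them.

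For VO2peak it assigns the Day 29 value or, failing that, baseline. Neither contains any effect of hormone therapy, yet Section 12.6 expects a fall of 2.0 mL/kg/min under that therapy and Section 9.5 describes the expected deterioration as rapid. For the three functional tests it assigns a change of exactly zero, with no spread, and counts it as if observed.

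The plan has little else to fall back on. Section 12.4.3 offers a second sensitivity analysis that interpolates to a VO2peak taken after week 17, but no such test is scheduled. In practice LOCF is the only working sensitivity analysis for the primary endpoint. The revised design also gives no allowance for loss: 40 men are to be enrolled (Section 6.1) and 40 evaluable men are needed (Section 12.6). A report that the result was robust because LOCF agreed with it would not be supported.

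**Working it through.** **Inputs from the documents.** The original design in Section 12.6 assumes a 16-week change of -2.0 in Arm A (usual care) and +1.0 in Arm B (exercise), an SD of 3.5 and 15% loss. The revised design has 20 evaluable per arm, one-sided alpha 0.10 and an effect size of 0.68. It restates neither the arm-level changes nor a loss rate, so the original values are borrowed here; 15% of 20 is 3 men.

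**Inputs assumed.** The Day 29 gain g in Arm B is not stated; I use 0.25 to 1.0. The Arm A change at Day 29 is taken as 0, because those men are asked not to change their activity. Observed men follow the design means.

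**Plan's own figures first.** The difference is 1.0 - (-2.0) = 3.0. With 23 per arm and SD 3.5, two-sided 0.05, noncentral-t power is 81.1%, and 23/0.85 = 27.06 rounds up to 28 per arm. For the revised design, power is 80.1%. Both reproduce.

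**Formulas.** Let fA and fB be the shares with no week-17 test.

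- LOCF difference = [(1 - fB)(1.0) + fB·g] - [(1 - fA)(-2.0) + fA·0]
- Target 1, missing Arm B men follow the Arm A course: [(1 - fB)(1.0) + fB(-2.0)] - (-2.0) = 3.0 - 3.0·fB
- Target 2, missing Arm B men keep +1.0: 3.0
- LOCF minus target 1 = fB(2 + g) - 2·fA

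**Results (complete-case difference is 3.00 throughout).**

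| Loss | LOCF | Target 1 | Target 2 |
|---|---|---|---|
| 3/20 in B only | 0.85 + 0.15g + 2.00 = 2.89 to 3.00 | 2.55 | 3.00 |
| 15% in each arm | 0.85 + 0.15g + 1.70 = 2.59 to 2.70 | 2.55 | 3.00 |
| 3/20 in A only | 1.00 + 1.70 = 2.70 | 3.00 | 3.00 |

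Against target 1, LOCF is 13% to 18% high in the first row, about 1.5% to 6% high in the second and 10% low in the third. Against target 2 it is equal or low in every row.

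The first and third rows show the problem best. With loss in Arm B only, LOCF stays close to the complete-case 3.00 although target 1 is 2.55. With loss in Arm A only, LOCF moves away from 3.00 although 3.00 is the target. Neither agreement nor disagreement is informative.

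**Effect on the test.** In 40,000 simulated trials (20 per arm, SD 3.5, true week-17 change -2.0 in both arms, g = 1), the one-sided 0.10 test under LOCF rejected 12% of the time with 15% missing in each arm. It rejected 23% with 25% missing in B and 5% in A, and 5% with those shares reversed. The 25% and 5% shares are illustrative.

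**Key secondary tests.** Let a and b be the Arm A and Arm B changes and f an equal loss share. LOCF gives (1 - f)b - (1 - f)a = (1 - f)(b - a). Target 1 gives (1 - f)b + f·a - a = (1 - f)(b - a). The two are identical. What remains against LOCF here is the zero spread and, under unequal loss, a gap of (fA - fB)·a.

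**The case against.** The case on the other side is substantial.

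- A reader might infer that LOCF favours exercise. The documents do not support that. It needs a lead-in gain, which Section 9.5 only hypothesizes as a buffer and does not quantify, and it needs exercise losses that are not clearly smaller than usual-care losses. If Arm A loses more men, or missing Arm B men would have kept the planned benefit (with g no larger than 1.0), LOCF understates the effect. Men lost before Day 29 are credited with nothing.
- A reader might also infer that LOCF always confirms the complete-case result. It does not: loss in Arm A pulls it away from 3.00.
- A third tempting reading is that multiplying a key secondary difference by 0.85 under equal 15% loss is itself a distortion. It is the same point estimate a control-based rule would give.
- The -2.0, +1.0 and 15% figures belong to the superseded calculation, and target 1 is an assumption.
- For the functional tests, imputation from baseline has no later data to draw on and will largely reproduce the complete-case estimate.
- This is a supporting analysis in a pilot, with perhaps three missing men per arm.

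All of this stands, and it limits the claim about direction and size. It does not rescue LOCF: a bias whose sign depends on unseen loss patterns is a reason not to use the rule as a robustness check. The Day 29 window of ±3 days may place a few tests just after the first dose; that is immaterial.

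**Conclusion.** The point holds as a statement about what the check can show. On the documented schedule, LOCF can fill week 17 only with a value taken at or before the start of enzalutamide plus ADT, so it cannot test the robustness that Sections 5 and 12.5 assign to it.

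On the original design's changes, with an assumed Day 29 gain of 0.25 to 1.0 and missing Arm B men following Arm A, the error runs from about 0.45 mL/kg/min too high (loss of 3/20 in Arm B, g = 1.0) to 0.30 too low (loss of 3/20 in Arm A). It is small, 0.04 to 0.15, under equal 15% loss. The documents support no claim that LOCF consistently favours exercise or consistently reproduces the complete-case result. The primary test does not depend on LOCF, so the priority is moderate to low.

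**What to change.** In Sections 5 and 12.5, replace LOCF with two analyses in all randomized men who have a baseline value, analysed as randomized:

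1. **Multiple imputation of the week-17 value by arm.** For VO2peak, use baseline, Day 29 VO2peak where available, and site. For chair stand and timed up-and-go, use baseline and site. For 6-minute walk, use baseline only, since it is measured at Duke alone.
2. **One departure analysis.** Use either a control-based version, in which missing Arm B men take the Arm A change, or a delta-adjusted (tipping-point) version, which shifts the imputed values for missing men until the conclusion changes. Choose one in advance. For the functional tests this is the analysis that does the real checking.

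Report the number missing by arm, and whether each man was lost before or after Day 29, beside the results.

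The cost is SAP wording and modest programming, with no new visits or data. Intervals will be wider than under LOCF, because LOCF treats guessed values as observed.

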9 SCREENING, REGISTRATION, AND ON-STUDY TESTS AND PROCEDURES

In addition to assessment for the **primary** endpoint (VO₂peak) by cardiopulmonary exercise testing (CPET), **secondary** and **exploratory** assessments for functional capacity, quantitative skeletal muscle function, metabolic, patient-reported outcomes, PSA, and metabolomics endpoints will occur throughout the study as specified below in the Schedule of Events.

The important time periods during the study include:

- **Screening** on Day -42 to randomization
- **Exercise Testing on Day -30 to randomization**
- **Randomization on Day -14 to Day 1, but after exercise testing (specifically, CPET) is complete**
- **Lead-In** of Usual Care (UC) or Exercise Training starting on Day 1
- **Treatment Period 1:** Enzalutamide + ADT with either UC or Exercise Training from Day 29 to 113
- **Treatment Period 2:** Enzalutamide + ADT from Day 114 to 252
- **End of treatment/Safety Follow-Up** within 30 days after the last dose of enzalutamide or prior to initiation of cytotoxic or investigation therapy, whichever occurs first

All subjects will receive treatment with ADT + enzalutamide for 32 weeks.

In addition, subjects randomized to Exercise Training (Arm B) will undergo a 16 week combined aerobic and resistance exercise training program, including a 4 week Lead-In before starting therapy with ADT + enzalutamide and during the first 12 weeks of therapy with ADT + enzalutamide.

SCHEDULE OF EVENTS

Phase		Screen	Baseline Exercise Testing ^{c,p}	4 Week Lead-In ^p		Treatment Period 1: Enzalutamide + ADT +/- Exercise Training				Treatment Period 2: Enzalutamide + ADT and Safety Follow-up	Unscheduled Visit ^a
				2	3	4					
Clinic Visit Number		1				2	3	4	5 (EOT) SEE NOTE		
Day		-42 to randomization	-30 to randomization	1 ^q	22	29	57	64	113	252	
Week		-6 to -1		1	4	5	9	10	17 ^a	37 ^a	
Window (Days)		NA		NA	+6	±3	±7	±3	±7	-7, +30	NA
General Evaluations	See Section										
Informed Consent ^b	9.2.1	X									
Eligibility Criteria	8	X									
Medical History	9.12.1	X									
Randomization ^c	6.1.4			X ^c							
Physical Exam ^d	9.12.2	X				X	X		X	X	X
Height, Weight, BMI	9.12.2	X				X	X		X	X	X
Vital Signs ^e	9.12.2	X				X	X		X	X	X
Performance Status (ECOG) ^f	App. A	X				X	X		X	X	X
Concomitant Medications	6.1.3	X				X	X		X	X	X
Adverse Events ^g	10	X				X	X		X	X	X
Laboratory Evaluations											
CBC with platelets ⁱ	9.1-9.7	X ⁱ				X	X		X	X	X ^h
Serum Chemistry ⁱ	9.1-9.7	X ⁱ				X	X		X	X	X ^h

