- g. Exercise-related adverse events will be collected from baseline/screening through the End of Study visit for all subjects. All other adverse events will be collected from the start of study drug. Serious adverse events are recorded from the time the informed consent form is signed until the Safety Follow-Up visit (or screen failure). In the event of no Safety Follow-Up visit, adverse event information will be collected through 30 days after the last dose of study drug. Subjects should be contacted by phone for adverse event follow-up if they do not come to the clinic for the Safety Follow-Up visit.
- h. Clinical laboratory tests may be performed at unscheduled visits if clinically indicated.
- i. Labs performed as part of screening are good for 30 days before randomization and do not need to be repeated.
- j. PSA may be performed at Unscheduled Visits as indicated to confirm PSA progression. No subject should discontinue study drug due to PSA rise during the first 12 weeks of therapy. Subjects with PSA progression on or after Week 17 must have progression confirmed by a second consecutive assessment conducted at least 3 weeks later before study drug discontinuation.
- k. CT of the abdomen and pelvis and bone scans should be performed to document that there is no definite evidence of metastatic disease at the time of screening. MRI of the abdomen and pelvis may be used in place of the CT.
- l. Baseline imaging performed per NCCN Guidelines⁸⁶ prior to informed consent as standard of care may be used so long as it is performed within 84 days prior to randomization.
- m. ADT (GnRH analogue) will be administered as per standard of care to maintain a castrate level of serum testosterone (<50 ng/dL) from Day 29 to Day 252.
- n. Muscular Strength and Muscular Endurance must be done at least 24 hours before or after CPET to allow adequate recovery time.
- o. Both the usual care group and the exercise training group will have a 4 week lead-in before starting ADT plus enzalutamide; only the exercise training group will undergo exercise training during this time.
- p. Day 1 is defined as the randomization day for Arm A (non-exercise) and the start of exercise for Arm B.
- q. Randomization may be done on Day 1 prior to the patient's exercise training session(s) for that week.
- r. DEXA scan for body composition should be fasting, if possible.

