9.7 Treatment Period 2: ENZ-ADT

Subjects on both arms will continue ADT per standard of care and enzalutamide through Week 37 (Day 252).

The window is -7/+30 days for this period. See **Schedule of Events**, above.

Subject data to be collected during Treatment Period 2 includes:

- Physical Exam
- Height, Weight, BMI
- Vital Signs
- Performance Status (ECOG)
- Concomitant Medications
- Adverse Events
- CBC with Platelets (hemoglobin, hematocrit, platelet count, white blood cell count, total [absolute] neutrophils)
- Serum Chemistry (sodium, potassium, chloride, total CO₂ [bicarbonate], calcium, BUN, creatinine, glucose, albumin, total bilirubin, total protein, alkaline phosphatase, AST, ALT)
- Testosterone (Day 169 and 252)

- PSA
- FACT-P (Day 252)
- FACIT-Fatigue (Day 252)
- Godin Leisure Time Exercise Questionnaire (Day 252)
- Collect Pill Diary for Enzalutamide

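### AE rates are planned per arm with no time period, which dilutes, but does not remove, an AE difference that arises during exercise training

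*Combined protocol and SAP*

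**What the plan says.** The only AE display in the combined protocol and SAP is in Section 12.5: "Rates of adverse events, classified by CTCAE v4.0, will be displayed by body system and preferred term for each arm". It gives no period of onset and no time at risk.

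Section 5 lists the AE rate in each arm among the Other Secondary endpoints, under the objective "Evaluate safety, feasibility, and acceptability of exercise training".

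Section 9 sets the exposure. "All subjects will receive treatment with ADT + enzalutamide for 32 weeks". The first stretch on drug is "Enzalutamide + ADT with either UC or Exercise Training from Day 29 to 113", and the second, the same for both arms, is "Enzalutamide + ADT from Day 114 to 252". Arm B also trains during the four-week lead-in before Day 29.

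On collection, footnote g of the Schedule of Events takes exercise-related AEs from baseline. For the rest it states "All other adverse events will be collected from the start of study drug". Under Section 10.1, enzalutamide-related AEs are collected to the Safety Follow-up visit.

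Section 12.5 does have a two-period rule (baseline to week 17, then week 17 to the end of week 36), with the second period meant to show a lasting effect. It is worded for changes in secondary and exploratory endpoints.

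**The concern.** The AE rate is meant to describe the safety of training, but on a plain reading of Section 12.5 it would be one rate per arm, built mostly from weeks in which nobody trains under the protocol. If training has no lasting effect, events after Day 113 occur at the same rate in both arms and pull the contrast towards no difference. This works in both directions. It would understate a harm of training during androgen suppression, and it would understate a reduction in fatigue or generalized muscle weakness, the two AEs of special interest in Section 10.1.1.

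The two-period rule does not clearly close the gap. It compares changes from one time point to another, and an AE rate has no baseline value from which to form a change. Section 12.4.2 splits VO2peak into lead-in, training on drug and post-training periods, so the plan already treats these as separate questions. The AE display does not carry that over.

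**Working it through.** **1. Exposure, from the days in Section 9.**
- On drug: 252 − 29 + 1 = 224 days = 32.0 weeks, which reproduces the stated 32 weeks.
- Training while on drug: 113 − 29 = 84 days = 12 weeks, or 84/224 = 37.5%.
- Same assigned treatment: 252 − 114 + 1 = 139 days = 19.9 weeks, or 139/224 = 62%.
- With the −7/+30 day window on Day 252: 132/217 = 61% to 169/254 = 67%.

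**2. Illustration on the risk scale.** Sections 4.3 and 6.3 give fatigue in 34.3% of men in a phase II study of enzalutamide monotherapy. They do not say over what time. Assumptions: accrual over 25 weeks (the time point Section 6.3 gives for that study's metabolic results), constant hazard, and an effect of training only while training.
- Hazard: h = −ln(1 − 0.343)/25 = 0.0168 per week.
- Arm A: 1 − exp(−12h) = 18.3% at 12 weeks; 1 − exp(−32h) = 41.6% at 32 weeks.
- Arm B with hazard ratio HR: 1 − exp(−12h·HR) at 12 weeks; 1 − exp(−h(12·HR + 20)) at 32 weeks.

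| HR while training | Day 29–113, A v B | Risk ratio; difference | 32 weeks, A v B | Risk ratio; difference |
|---|---|---|---|---|
| 0.5 | 18.3% v 9.6% | 0.53; 8.7 points | 41.6% v 35.4% | 0.85; 6.2 points |
| 2.0 | 18.3% v 33.2% | 1.82; 14.9 points | 41.6% v 52.3% | 1.26; 10.7 points |

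The risk difference keeps 6.2/8.7 = 71% and 10.7/14.9 = 72% of its size. In an arm of 20, 8.7 and 6.2 points are about 1.7 and 1.2 men.

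If 34.3% is instead taken as the 32-week risk in Arm A, a halved hazard gives 14.6% v 7.6% to Day 113 and 34.3% v 28.9% pooled.

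**3. Event rates rather than risks.** With a constant rate and no carry-over, the pooled rate ratio is (12·RR + 20)/32. A true ratio of 0.50 becomes 26/32 = 0.81, and 2.0 becomes 44/32 = 1.38.

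**4. Timing and carry-over.** If a share f of control events falls in the first 12 weeks and there is no carry-over, the pooled ratio is f·RR + (1 − f).
- f = 0.7: 0.50 becomes 0.65, and 2.0 becomes 1.7.
- f = 0.9: 0.50 becomes 0.55, and 2.0 becomes 1.9.
- Constant rate, with half the effect (log scale) lasting after Day 113: 0.50 becomes 0.63.
- Full carry-over: 0.50 stays 0.50.

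**5. Power.** With 20 per arm, two-sided 0.05, a 32-week risk of 34.3% in Arm A and a halved hazard, power is about 10% for Day 29–113 and 6% pooled.

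**The case against.** The strongest reply is that little turns on this. No AE test is planned, power is low with or without a split, and most of the absolute difference survives pooling in the example. The AE sentence is silent on period rather than committed to pooling, and since AE rate is a secondary endpoint, one could argue that the two-period rule applies. Other data also help. Attribution to drug, training or testing is recorded (Section 10.1). Fatigue is measured by FACIT-F at baseline, Day 113 and Day 252, and strength is tested at baseline and at weeks 4, 10 and 17.

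Most of this stands, and it limits the point to a minor one. It does not remove it. Section 12.5 does not say that the rule covers AEs or that attribution will be tabulated, and attribution cannot show a reduction in events. In purely descriptive data, the displayed contrast is what readers will interpret.

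A reader might also infer that the pooled table hides any effect of exercise on AEs, or that events after Day 113 are only noise. The documents support neither. The effect is weakened by an amount that depends on event timing and carry-over, which they do not give. Whether training has a lasting effect is a stated question of the trial, so the later events are informative in their own right.

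It is tempting, too, to compare all AEs from Day 1 to Day 113. Collection does not allow it: before first dose, non-serious AEs are recorded only if exercise-related. A comparison between arms in that window would be incomplete, and it could make training look harmful because only Arm B trains.

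**Conclusion.** The AE display in Section 12.5 lacks a period, and the arms' assigned treatment differs on drug for only about 12 of 32 weeks. A single pooled rate per arm dilutes an on-training difference but does not remove it. At a constant hazard without carry-over, the risk ratio moves from 0.53 to 0.85 or from 1.82 to 1.26, and roughly 70% of the risk difference remains. These sizes rest on a monotherapy fatigue figure, an assumed 25-week accrual and an effect that stops at Day 113. Early events or a lasting effect make the dilution smaller, down to none with full carry-over. The day counts and the missing period come straight from the documents and need no assumption. This is a minor reporting point that leaves the primary analysis untouched.

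**What to change.** Amend Section 12.5 to display AE rates by arm and period of onset, with the number of men or the person-time at risk in each period:
- **First dose (Day 29) to Day 113:** the main all-cause comparison for the safety of exercise training.
- **Day 114 to the Safety Follow-up visit:** shown separately, for any lasting effect.
- **Lead-in:** shown separately, for exercise-related AEs and SAEs only. Footnote g records SAEs from consent, while Section 10.1 limits SAEs before first dose to those related to study exercise procedures, so the table should state which it includes.

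Count each man once per preferred term per period, by onset date. Keep the whole-study table as a summary. Fix the periods before AE data are reviewed by arm, because the trial is open label (Section 6.1.4) and a window chosen afterwards invites doubt.

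The cost is a few lines of SAP text and some extra tables from onset dates, with no new visits, data or patients. The downsides are more descriptive tables with small counts, and a post-Day 113 denominator that is a post-randomisation subset, so that table needs a caution.
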